1.6.2. B7451005 Study Data

Preliminary results of biomarkers (IP-10 and hsCRP) showed rapid reduction in all active treatment groups. The effect was more pronounced in the BID than the QD groups.

1.7. Summary of Benefits and Risks

The anticipated risks associated with PF-04965842 in relation to anemia are minimal because erythropoietin signals through the JAK2 dimers. Thus, in comparison to pan-JAK inhibitors, PF-04965842's selectivity to erythropoietin may provide clear advantage in regard to anemia. However, the 10-day dosing duration in the Phase 1 study B7451001 was not long enough to test for anemia. Also, PF-04965842's lesser effect on IL-15 which is linked to non-killer (NK) cells may provide further differentiation from pan-JAK inhibitors and may prove to be beneficial in terms of lesser effect on immune functions related to viral infections and tumor surveillance.

Overall, the safety profile observed during the Phase 1 program for PF-04965842 appears to be acceptable at dosages of up to 800 mg administered as a single dose and up 400 mg when administered as repeat doses of either 400 mg QD or 200 mg BID. The preliminary data from the 4 week POC Pso study showed that PF-04965842 appeared generally well tolerated up to 400 mg QD or 200 mg BID. The data generated in the development program to date support the further development of PF-04965842 and its advancement to a POC study in AD.

1.8. Rationale

1.8.1. Study Rationale

PF-04965842 is a selective inhibitor of JAK1. The selective inhibition of JAK1 will lead to modulation of multiple cytokines which play a critical role in the pathogenesis of AD (eg, IL-4, IL-13, IL-17, IL-22, IL-31, and IFN γ). Dupilumab, a fully human monoclonal antibody that blocks the activity of IL-4 and IL-13 signaling, has shown efficacy in patients with AD.² Systemic treatment with dupilumab in adults with moderate to severe AD resulted in marked reductions in signs and symptoms of AD, and associated biomarker levels. Topical tofacitinib, a pan JAK inhibitor, recently completed a 4 week Phase 2a trial that demonstrated the efficacy of JAK inhibition in mild to moderate AD (study A3921214). In this study, significantly greater efficacy was observed with topical tofacitinib vs. vehicle in reducing the signs and symptoms of AD, with a suitable safety and local tolerability profile. In addition, oral tofacitinib has shown therapeutic effect in 6 patients with recalcitrant AD.¹⁰

JAK1-selective inhibitors such as PF-04965842, spare dose-limiting effects of pan-JAK inhibition by preserving JAK2 homodimer signaling and thus provide the potential for safer and efficacious oral treatments for AD. Oclacitinib, a JAK1 inhibitor, has already demonstrated efficacy and is approved for the treatment of canine atopic dermatitis.⁴

B7451006 is a Phase 2b study to evaluate the efficacy and safety of PF-04965842 in comparison to placebo in patients with moderate to severe atopic dermatitis using the Investigator Global Assessment.

Clinical evaluations of AD in this study will include Investigator Global Assessment (IGA), Eczema Area and Severity Index (EASI), Body Surface Area (BSA) involvement, and SCORing Atopic Dermatitis (SCORAD).

PF-04965842 efficacy will also be evaluated via patient reported outcomes (PROs): Pruritus numerical rating scale (NRS) score, Patient Global Assessment (PtGA), Dermatology Life Quality Index (DLQI), Patient Oriented Eczema Measure (POEM), CCI [REDACTED] and Hospital and Anxiety Depression Scale (HADS).

The study will provide samples for exploratory analysis of pharmacodynamic biomarkers for JAK1 inhibition such as IP-10 (CXCL10), hsCRP, CCL17 (TARC), IL-31, total IgE. Samples will also be collected for flow-cytometric (fluorescence-activated cell sorting [FACS]) assessment of lymphocyte subsets.

1.8.2. Dose Selection Rationale

This Phase 2b study will evaluate the efficacy and safety of PF-04965842 in patients with moderate to severe AD. The study will assess 4 PF-04965842 doses of 10 mg, 30 mg, 100 mg and 200 mg administered orally once daily (QD) for 12 weeks. Listed in Table 1 are the predicted geometric mean (%CV) PK parameter values following QD dosing for 12 weeks which were derived from population PK modeling of the human PK data from the FIH study (B7451001).

Table 1. Predicted Geometric Mean PK Parameters following QD Dosing

Dose mg QD x 12 weeks	Geometric Mean		Safety Margins ^a	
	C _{max,ss} ng/mL	AUC _{tau} ng.hr/mL	C _{max,ss}	AUC _{tau}
10	33.2(9)	83.7 (33)	156	659
30	135.0 (9)	386 (36)	38	143
100	632.6 (7)	2197 (39)	8.1	25
200	1525 (6)	5928 (37)	3.4	9.3

() = % coefficient of variation; AUC_{tau} = Area under the concentration-time curve over the dosing interval 0-24 hours; C_{max,ss} = Peak plasma concentration at steady state; QD = Once daily

^a NOAEL in cynomolgus monkeys, 75 mg/kg/day; Day 273 combined male and female total C_{max,ss} = 1910 ng/mL; total AUC_{tau} = 55200 ng•h/mL.

The doses selected for this study are supported by significant safety margins from the repeat dose toxicity study up to 9 months in monkeys. The dose range should allow

characterization of the dose response for efficacy over a 20-fold range and anchoring at the lower end with a minimally effective dose.

The selective inhibition of JAK1 will lead to modulation of multiple cytokine pathways implicated in the pathophysiology of AD, eg IL-4, IL-13, IL-17, IL-22, IL-31, and INF γ . In study B7451001, mechanistic biomarkers hsCRP and IP-10 related to IL-6 and INF γ , respectively, were measured in healthy subjects.

A classic indirect response model was used to estimate the reduction of hsCRP, IP-10 and safety biomarkers (neutrophils, platelets and reticulocytes) as well as to project the potential impact on signaling of the various cytokines that may be associated with efficacy in AD over a range of PF-04965842 exposures (Table 2). The baseline values for hsCRP, IP-10 and safety biomarkers (neutrophils, platelets and reticulocytes) in subjects with AD are comparable to those observed in healthy subjects and subjects with psoriasis. The modeling predicts maximum percent reduction for the safety biomarkers in the absence of compensatory mechanism due to short duration of the studies conducted to date.

Table 2. Modeled Predicted Geometric Mean Percent Reduction in Pathways Signaling and Biomarkers

	10 mg	30 mg	100 mg	200 mg
IL-4	0.26	1.20	5.83	12.9
IL-4 HT-29	1.21	4.74	18.4	34.5
IL-13	0.35	1.57	7.45	16.2
IL-13 HT-29	1.31	5.18	20.3	37.6
IL-22	0.31	1.41	6.68	14.5
IL-31	2.58	9.28	31.3	51.7
hsCRP	9.02	23.0	43.3	59.1
IP-10	1.31	4.64	14.0	23.8
Neutro-phiils	0.11	0.50	2.36	5.71
Reticulo-cytes (Abs)	0.96	4.59	18.3	32.8
Platelets	0.78	3.63	11.6	26.9

As previously described there are multiple cytokines involved in the manifestation of AD, thus, the main driver of disease or the relative contribution of the cytokines to efficacy is not understood. However, Dupilumab an antibody to the receptors for IL-4 and IL-13 has demonstrated efficacy in AD. In study B7451005, in subjects with psoriasis, which evaluated 200 mg and 400 mg QD and 200 mg BID of PF-04965842 for 28 days, all active treatments decreased itch severity score at 7 days post dose, the first evaluation timepoint. IL-31 has a pivotal role in itch manifestation in AD and modeling predicted approximately a 52% reduction of IL-31 stimulation of Signal Transducers and Activators of Transduction (PSTAT)-6 signaling by the 200 mg QD dose.

Preliminary assessment of safety data from study B7541005 showed that the majority of the hematological laboratory abnormalities occurred in the 200 mg BID group. Based on this finding a BID regimen will not be evaluated in AD. Reductions in absolute reticulocyte

090177e18dabc380\0.1\Draft\Versioned On:07-Feb-2018 09:59 (GMT)

count were observed at all dose levels with the maximum mean % decrease occurring in the 200 mg BID group (57.3%) compared to 21.5% and 17.9% in the 400 mg QD and 200 mg QD groups, respectively. There were platelet reductions in all active treatment groups. Platelet counts $<100,000/\text{mm}^3$ were observed in the 400 mg QD and 200 mg BID cohorts, with the majority of cases occurring in the BID cohort. There were no cases of platelet counts $<100,000/\text{mm}^3$ in the 200 mg QD group. No bleeding events relative to thrombocytopenia were reported during the clinical trial.

The projected reductions suggest that at least 1 dose should be active with acceptable safety and tolerability appropriate for the long term treatment of adult subjects with moderate to severe AD.

2. STUDY OBJECTIVES AND ENDPOINTS

2.1. Primary Objectives

- The primary objective of this study is to evaluate the efficacy of 4 QD dose levels (10, 30, 100, and 200 mg) of PF-04965842 relative to placebo in adult subjects with moderate to severe atopic dermatitis, using the Investigator's Global Assessment (IGA).

2.2. Secondary Objectives

- To evaluate the effect of PF-0465842 on additional efficacy endpoints and patient reported outcomes over time in adult subjects with moderate to severe atopic dermatitis.
- To evaluate the safety and tolerability of PF-0465842 over time in adult subjects with moderate to severe atopic dermatitis.

2.3. CCI [REDACTED]

- CCI [REDACTED]
- [REDACTED]

2.4. Endpoints

2.4.1. Primary Endpoints

- Proportion of subjects achieving the IGA for clear (0) or almost clear (1) and ≥ 2 points improvement from baseline at Week 12. The baseline will be defined as the IGA score on Day 1 pre-dose.

2.4.2. Secondary Endpoints

2.4.2.1. Efficacy Endpoints

Baseline is defined as the score for each assessment on Day 1 pre-dose.

2.4.2.1.1. Key Secondary Efficacy Endpoint

- Percent change from baseline in the eczema area and severity index (EASI) Total score at Week 12.

2.4.2.1.2. Secondary Efficacy Endpoints

- Proportion of subjects achieving the IGA for clear (0) or almost clear (1) and ≥ 2 points improvement from baseline at all scheduled time points except Week 12.
- Percent change from baseline in the EASI total score at all scheduled time points except Week 12.
- Proportion of subjects achieving ≥ 3 points improvement in the pruritus numerical rating scale (NRS) from baseline at all scheduled time points.
- Percent change from baseline in the pruritus NRS from baseline at all scheduled time points.
- Proportion of subjects achieving ≥ 2 points improvement in the IGA from baseline at all scheduled time points.
- Proportion of subjects achieving a $\geq 50\%$, 75% and 90% improvement in the EASI Total score (EASI50, EASI75, EASI90) at all scheduled time points.
- Change from baseline in affected body surface area (BSA) at all scheduled time points.
- Change from baseline in SCORing atopic dermatitis (SCORAD) at all scheduled time points.
- Proportion of subjects achieving a $\geq 50\%$ and 75% improvement in SCORAD (SCORAD50, SCORAD75) from baseline at all scheduled time points.

2.4.2.2. Safety Endpoints

- Incidence of treatment-emergent adverse events.
- Incidence of specific clinical laboratory abnormalities (anemia, neutropenia, thrombocytopenia, lymphopenia, lipid profile, liver function tests [LFTs]).

2.4.2.3. Patient-Reported Outcome (PRO) Endpoints

Baseline is defined as the score for each assessment on Day 1 pre-dose.

- Change from baseline in Pruritus NRS score at all scheduled time points.

- Proportion of subjects with patient global assessment (PtGA) of AD of clear (0) or almost clear (1) and ≥ 2 points improvement from baseline at all scheduled time points.
- Change from baseline in dermatology life quality index (DLQI) total score at all scheduled time points.
- Change from baseline in patient Oriented Eczema Measure (POEM) at all scheduled time points.
- Change from baseline in the hospital and anxiety depression scale (HADS) at all scheduled time points.

[figure not shown]
2.4.3. CCI [REDACTED]

- CCI [REDACTED]
- [REDACTED]
- [REDACTED]

3. STUDY DESIGN

This Phase 2b, multi-center, randomized, double-blind, 5-arm, parallel group study will enroll a total of approximately 250 subjects (providing approximately 200 completers, 40 subjects per treatment group). The study will be conducted at approximately 60 sites.

Figure 1. Study Design Schematic

090177e18dabc380\0.1\Draft\Versioned On:07-Feb-2018 09:59 (GMT)

Subjects who have chronic AD that has been present for at least 1 year (prior to screening visit) and affected BSA of $\geq 10\%$, EASI ≥ 12 and IGA ≥ 3 at the screening and baseline visits will be included in the study. Subjects must also have a documented history of inadequate response to treatment with topical medications given for at least 4 weeks, or for whom topical treatments are otherwise medically inadvisable (eg, because of important side effects or safety risks) within 12 months of the first dose of study drug. Subjects will be randomized to 1 of 4 treatment groups or placebo in the ratio of 1:1:1:1. Investigators, subjects, and the sponsor study team will be blinded as to treatment group.

Subjects will be screened within 35 days prior to the first dose of study drug to confirm that they meet the subject selection criteria for the study. There will be a 12-week double-blind treatment period as well as a 4-week follow up period.

An interim analysis may be performed when approximately a total of 110 randomized subjects complete 6 weeks of study or discontinue prematurely from study in order to assess the percent change of EASI score from baseline as well as other safety and efficacy endpoints such as IGA response as appropriate. Please refer to [Section 9.4](#) for details.

4. SUBJECT SELECTION

This study can fulfill its objectives only if appropriate subjects are enrolled. The following eligibility criteria are designed to select subjects for whom participation in the study is considered appropriate. All relevant medical and nonmedical conditions should be taken into consideration when deciding whether a particular subject is suitable for this protocol.

4.1. Inclusion Criteria

Subject eligibility should be reviewed and documented by an appropriate member of the investigator's study team before subjects are included in the study.

Subjects must meet all of the following inclusion criteria to be eligible for enrollment into the study:

1. Evidence of a personally signed and dated informed consent document indicating that the subject has been informed of all pertinent aspects of the study.
2. Male or female subjects between 18-75 years of age, inclusive, at time of informed consent.
3. Subjects who are willing and able to comply with scheduled visits, treatment plan, laboratory tests and other study procedures.
4. Male subjects able to father children and female subjects of childbearing potential and at risk for pregnancy must agree to use a highly effective method of contraception (per [Section 4.4.2](#)) throughout the study and for at least 28 days after the last dose of assigned treatment.

Female subjects who are not of childbearing potential (eg, meet at least 1 of the following criteria):

- Have undergone a documented hysterectomy and/or bilateral oophorectomy;
 - Have medically confirmed ovarian failure; or
 - Achieved postmenopausal status, defined as follows: cessation of regular menses for at least 12 consecutive months with no alternative pathological or physiological cause; status may be confirmed by having a serum follicle stimulating hormone (FSH) level confirming the post-menopausal state.
5. Must have the following atopic dermatitis criteria:
- a. Have a clinical diagnosis of chronic atopic dermatitis (also known as atopic eczema) for at least 1 year prior to Day 1 and has confirmed atopic dermatitis (Hanifin and Rajka criteria of AD refer to [Appendix 2](#)) at the Screening visit.
 - b. Have inadequate response to treatment with topical medications given for at least 4 weeks, or for whom topical treatments are otherwise medically inadvisable (eg, because of important side effects or safety risks) within 12 months of the first dose of study drug.
 - c. Moderate to severe AD (affected BSA $\geq 10\%$, IGA > 3 , and EASI > 12 at the screening and baseline visits).
6. Must agree to avoid prolonged exposure to the sun and not to use tanning booths, sun lamps or other ultraviolet light sources during the study.
7. If receiving concomitant medications for any reason other than AD, must be on a stable regimen, which is defined as not starting a new drug or changing dosage within 7 days or 5 half-lives (whichever is longer) prior to Day 1. Subject must be willing to stay on a stable regimen during the duration of the study.

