
- CCI [REDACTED]

CCI [REDACTED]

- [REDACTED]
- [REDACTED]

Study Design:

This Phase 2b, multi-center, randomized, double-blind, 5-arm, parallel group study will enroll a total of approximately 250 subjects (providing approximately 200 completers, 40 subjects per treatment group). The study will be conducted at approximately 60 sites.

Subjects who have chronic AD that has been present for at least 1 year (prior to screening visit) and affected BSA of $\geq 10\%$, EASI ≥ 12 and IGA ≥ 3 at the screening and baseline visits will be included in the study. Subjects must also have a documented history of inadequate response to treatment with topical medications given for at least 4 weeks, or for whom topical treatments are otherwise medically inadvisable (eg, because of important side effects or safety risks) within 12 months of the first dose of study drug. Subjects will be randomized to 1 of 4 treatment groups or placebo in the ratio of 1:1:1:1. Investigators, subjects, and the sponsor study team will be blinded as to treatment group.

Subjects will be screened within 35 days prior to the first dose of study drug to confirm that they meet the subject selection criteria for the study. There will be a 12-week double-blind treatment period as well as a 4-week follow up period.

An interim analysis may be performed when a total of approximately 110 randomized subjects complete 6 weeks of study or discontinue prematurely from study in order to assess the percent change of EASI score from baseline as well as other efficacy and safety endpoints such as IGA response, pruritus NRS response and hematological parameters as appropriate. Modifications to the design such as adjustments to the final sample size or termination of enrollment of subjects in a treatment arm or stopping a treatment arm may be made upon review of the data. Unless a safety concern arises, no decisions to stop the trial will be made based on this interim analysis. Please refer to [Section 9.4](#) for details.

Study Treatments:

PF-04965842 will be administered orally at one of the following 4 doses: 10, 30, 100, or 200 mg administered QD for 12 weeks. In addition, one cohort will receive PF-04965842-matching placebo.

090177e18dabc380\0.1\Draft\Versioned On:07-Feb-2018 09:59 (GMT)

Statistical Methods:

Sample Size Determination

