4.3. Randomization Criteria

Subjects will be randomized into the study provided they have signed an informed consent document to participate in the study, have undergone all screening procedures, and have met all inclusion and none of the exclusion criteria for participation in the study at Day 1. A computer-generated randomization schedule will be used to assign subjects to the treatment groups using an Interactive Voice Response System (IVRS).

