7.6. Efficacy Assessments

7.6.1. Investigator Global Assessment (IGA)

The clinical evaluator of atopic dermatitis will perform an assessment of the overall severity of atopic dermatitis and assign an IGA score and category as described in [Table 3](#). The assessment will be a static evaluation without regard to the score at a previous visit.

Table 3. Investigator Global Assessment (IGA) Score

Score	Category	Description*
0	Clear	Atopic dermatitis is cleared, except for any residual discoloration (post-inflammatory hyperpigmentation and/or hypopigmentation).
1	Almost Clear	Overall, the atopic dermatitis is not entirely cleared and remaining lesions are light pink (not including post inflammatory hyperpigmentation) and/or; have barely palpable hard thickened skin and/or papules and/or; have barely perceptible lichenification; excoriation and oozing/crusting are absent.
2	Mild	Overall, the atopic dermatitis consists of lesions that are light red; with slight, but definite hard thickened skin and/or papules; with slight, but definite linear or picked scratch marks or penetrating surface injury; with slight, but definite thickened skin, fine skin markings, and lichenoid scale; oozing/crusting is absent.
3	Moderate	Overall, the atopic dermatitis consists of lesions that are red; with easily palpable moderate hard thickened skin and/or papules; with moderate linear or picked scratch marks or penetrating surface injury; with moderate thickened skin, coarse skin markings, and coarse lichenoid scale; with slight oozing/crusting.
4	Severe	Overall, the atopic dermatitis consists of lesions that are deep, dark red; with severe hard thickened skin and/or papules; with severe linear or picked scratch marks or penetrating surface injury; with severe thickened skin with very coarse skin markings and lichenoid scale; with moderate to severe oozing/crusting.

* The IGA will exclude scalp, palms, and soles from the assessment/scoring..

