5.5.2. Deviations Assessed Post-Randomization

Post-randomization deviations include:

- Subjects who receive excluded concomitant medications or rescue medications during the treatment period as described in Section 5.8 of the Protocol;
- Subjects who were randomized but took incorrect treatment;
- Subjects not satisfying the eligibility criteria, although, not identified until after randomization occurred.

Any significant deviation or violations from the protocol will be reviewed by the clinical team during the course of the study and prior to database closure and a decision taken regarding evaluation for each analysis set.

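### Inclusion criterion 5c asks for IGA above 3 and EASI above 12, while the synopsis, the design section and the SAP ask for at least 3 and at least 12; read literally, 5c admits only severe disease.

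*Protocol*

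**What the plan says.** Criterion 5c in Protocol 4.1 opens with the label "Moderate to severe AD (affected BSA" and then requires "IGA > 3 , and EASI > 12 at the screening and baseline visits". In the same line, the body surface area limit is set at greater than or equal to 10%.

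The protocol synopsis (Study Design) and Protocol section 3 describe the same entry condition differently: "EASI ≥ 12 and IGA ≥ 3 at the screening and baseline visits will be included in the study". SAP 2.1 gives the same limits as these two.

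Three places give section 4.1 its force:
- Its introduction says "Subjects must meet all of the following inclusion criteria to be eligible for enrollment into the study".
- Protocol 4.3 makes randomization conditional on subjects who "have met all inclusion and none of the exclusion criteria for participation in the study at Day 1".
- SAP 5.5.1 has the investigator assess subjects against Protocol 4.1 and 4.2.

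SAP 5.5.2 lists among the post-randomization deviations: "Subjects not satisfying the eligibility criteria, although, not identified until after randomization occurred". It adds that the clinical team reviews significant deviations before database closure and decides what they mean for each analysis set.

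**The concern.** One entry threshold has two incompatible values in current text, and the odd one out is in the list that sites must apply. On a five-point integer scale, the choice between strictly above 3 and at least 3 decides whether a whole severity category is in the trial.

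Two things are at stake. The first is who is enrolled: the primary objective (Protocol 2.1) concerns moderate to severe disease, and a literal 5c would supply only the severe part. The second is how enrolled IGA 3 subjects are classified. The SAP describes a population that includes them (2.1) but assesses eligibility against a section that excludes them (5.5.1). The study plans approximately 60 sites, so practice could also differ from site to site.

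**Working it through.** No power or sample size figure is involved. The check compares the texts and enumerates the scale.

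**1. The entry limits side by side**

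| Place | BSA | EASI | IGA |
|---|---|---|---|
| Protocol synopsis, Study Design | ≥ 10% | ≥ 12 | ≥ 3 |
| Protocol section 3 | ≥ 10% | ≥ 12 | ≥ 3 |
| SAP 2.1 | ≥ 10% | ≥ 12 | ≥ 3 |
| Protocol 4.1, criterion 5c | ≥ 10% | > 12 | > 3 |

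None of these is an amendment log. All four are current text.

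**2. What the IGA sign does.** Protocol 7.6.1, Table 3, gives scores 0, 1, 2, 3 and 4. Score 3 is the Moderate category ("Overall, the atopic dermatitis consists of lesions that are red; with easily palpable moderate hard thickened skin" and further signs), and score 4 is Severe.
- IGA > 3 gives {4}, Severe only.
- IGA ≥ 3 gives {3, 4}, Moderate and Severe.

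The strict sign removes the whole Moderate category.

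**3. What the EASI sign does.** Protocol 7.6.2 says that the EASI moves in steps of 0.1 from 0.0 to 72.0. The lowest score allowed by > 12 is 12.1, and by ≥ 12 it is 12.0. The two rules differ only for a subject scoring exactly 12.0.

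**4. What it does to the primary endpoint.** Response means an IGA of 0 or 1 with at least 2 points of improvement (Protocol 2.4.1).
- From baseline 3, the smallest qualifying fall is 3 − 1 = 2 grades.
- From baseline 4, the smallest qualifying fall is 4 − 1 = 3 grades.

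The sign therefore changes both who enters and how far a subject must improve to count as a responder.

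**5. What follows at a given site.** The consequences are alternatives:
- If the site applies 5c literally, moderate patients are excluded and everyone entered must fall at least 3 grades to respond. No IGA 3 deviations arise there.
- If the site applies section 3, IGA 3 subjects are enrolled and the population is as intended. Each of them is then literally an eligibility deviation under SAP 5.5.1 and 5.5.2.

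Mixed practice across sites would give some of each.

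**The case against.** The strongest reply is that the intent is plain. Criterion 5c carries a moderate-to-severe label, Table 3 defines 3 as moderate, and the objective, the synopsis, section 3 and SAP 2.1 all fit at least 3. On that view 5c contains a typing error, and nothing shows that any site acted on it. This stands as an account of the cause. It does not remove the need to correct the text, because 5c is the operative criterion and the SAP points to it when eligibility is assessed.

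A second reply is that the sign may be an artefact of reading the PDF: an underlined > can lose its underline. Operators elsewhere in this text are not fully reliable either. SAP 6.1.1 shows the 2-point improvement without a ≥ sign, while Protocol 2.4.1 and SAP Appendix 2 have it. The ≥ kept for body surface area in the same line of 5c makes a selective loss unlikely but does not rule it out. The source PDF should be checked first.

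A third reply concerns the analysis. The full analysis set (SAP 5.1) is all randomized subjects with at least one dose, less one named site, and the SAP defines no per-protocol set. A reader might infer that IGA 3 subjects would drop out of the primary analysis, but no stated rule removes them. What remains is that SAP 5.5.2 leaves significant deviations to review for each analysis set, and SAP 5.1 shows that exclusion for major deviations has been used, for 4 subjects at one site.

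**Conclusion.** The contradiction is real in the text as read and needs correcting. Criterion 5c, taken literally, limits entry to IGA 4 and conflicts with its own label, the primary objective and three other statements of the same limits. A drafting slip is the probable explanation. The IGA sign carries the point; the EASI sign is minor. The conclusion assumes that the source PDF shows the same strict signs in 5c.

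Three stronger conclusions might be inferred, and the documents support none of them:
- **A count of affected subjects.** Assuming that 40% to 70% of subjects have IGA 3 would give 0.40 × 250 = 100 to 0.70 × 250 = 175. Neither document gives a basis for that share, so the number affected is unknown.
- **Failed planning rates.** Protocol 9.1 assumes 10% on placebo and a 33-point difference, hence 43% on active. A 3-grade fall may be harder to reach than a 2-grade fall, but the documents give no response rate by baseline IGA and do not tie these rates to severity. The effect on the rates or on power cannot be shown.
- **A severe-only trial that is also full of IGA 3 deviations.** At any one site these exclude each other, and the documents do not show which wording sites applied.

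**What to change.** First check the signs in criterion 5c against the source PDF. If they are strict there, reconcile the synopsis, Protocol section 3, Protocol 4.1 (5c) and SAP 2.1, so that one IGA limit and one EASI limit, consistent with the stated moderate-to-severe population, appear in all four. State in the SAP that eligibility deviations are judged against the reconciled criterion, so that the status of IGA 3 subjects is settled before unblinding.

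The cost is small: a short protocol amendment, a notice to sites and one sentence in the SAP. Protocol 12.1 requires ethics committee or review board approval before an amendment takes effect, except to remove an immediate hazard, so that step has to be allowed for. The sample size and the analysis methods do not change.
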